4.2.4. Treatment of the treated lesion

Summary statistics or percentages and confidence intervals will be calculated by product for treatment of the treatment lesion specified below.

TABLE 11-1 TREATMENT OF TARGET LESIONS

- Analysis set: Stent implantation cases (newly enrolled patients)

Items * calculate summary statistics

No	Item name
1	Thrombus aspiration
2	Direct stent only
3	Direct stent + posterior dilatation
4	Pretreatment + stenting
5	Conditioning + stenting + posterior dilatation
6	Pretreatment direct stent (no pretreatment)
7	Pre-dilatation with pre-lesion treatment POBA
8	Lesion conditioning rotablator
9	Pre-dilatation with a pre-lesion conditioning cutting balloon
10	Pre-dilatation with a prelesion conditioning scoring balloon
11	Pretreatment of lesions, etc.
12	Post dilatation
13*	Maximum balloon diameter (mm)
14*	Maximum diastolic pressure (atm)

Table 11-2 Number of stents placed in target lesions

- Analysis set: Stent implantation cases (newly enrolled patients)

Items * calculate summary statistics

No	Item name
1*	Number of stents with target lesions (per lesion)
2*	Number of indwelling XP_SV Mean, standard deviation and sample size only calculated
3	XP_SV number placed 1 stent
4	Placed XP_SV number 2 stents
5	Implanted XP_SV number 3 stents
6*	Number of other stents placed Mean, standard deviation and sample size only calculated
7	Number of other stents placed 0 stents
8	No. of other stents placed 1 stent
9	Number of other stents placed 2 stents
10	Bailout stent
11*	Total length of stent placed (mm per lesion)

4.2.5. Bifurcation lesion information

The proportion and confidence interval of relevant cases will be calculated by product for the branching lesion information specified below.

Table 12. Branch lesion information

- Analysis set: Stent implantation cases (newly enrolled patients)

Items

No	Item name
1	Branched-lesion True
2	Branched-lesion False
3	Divergent lesion type unknown
4	Detailed retention below

4.2.6. Method of treating bifurcation lesions

For the method of treating bifurcation lesions, the proportion and confidence intervals of relevant cases will be calculated by bifurcation lesion type and product.

TABLE 13-1 METHODS OF TREATMENT OF FUNCTION LESIONS (FUNCTION LESIONS TYPE-True)

TABLE 13-2 METHODS OF TREATMENT OF FUNCTION LESIONS (FUNCTION LESIONS TYPE-False)

Table 13-3. Treatment of bifurcation lesions (bifurcation lesion type-all types)

- Analysis set: Stent implantation cases (newly enrolled patients)

Items

No	Item name
1	Provisional Stent [stenting in main branches only, Provisional T, Provisional Culottes]
2	Elective Stent [Classic T, Modified T, Crush, Culottes, Kissing Stent]
3	Kissing balloon

4.2.7. Use of stents

The XP_SV stents used will be summarized by diameter and length. Cross-tabulation of stent length × stent diameter is also performed.

Table 14. Number of stents used by size

Table 14-1. Breakdown of indwelling stents by size

- Analysis set: Stent implantation cases (newly enrolled patients)

Items

No	Item name
1	Diameter of the stent 2.25mm

No	Item name
2	Length of the stent 8 mm, 12 mm, 15 mm, 18 mm, 23 mm, 28 mm, 33 mm, 38 mm

4.2.8. Success rate

Success rates and confidence intervals will be calculated by product for per-device placement (XP_SV only), per-lesion procedure and per-patient XP_SV placement.

No	Items	Analysis set
1	Successful placement per device (XP_SV only)	Number of devices used by the study population cases
2	Successful procedure for each lesion	Number of lesions in the subject cases (only those for which lesion information is collected)
3	Successful XP_SV placement per patient	Number of subjects surveyed

Table 15. Success rate

- Analysis set: Surveyed patients (newly enrolled patients)

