2.2 Enrollment Method

- Patient informed consent is required for registration of this PMS In cases where patient informed consent (or providing some type of information) is required for PMS per the participating site policy, the Sponsor will cooperate as needed.
- If it is known at the time of index procedure that the patient is not able to return for the 8-month follow-up visit for angiogram and for the 1-year clinical follow-up, then the patient should not be registered in the PMS.
- Patients who are treated (stent delivery system inserted into the body) by XIENCE PRIME SV will be registered (including provisional stenting for side branch treatment but excluding bail-out only use)
 - The observations will be compiled on a per-patient basis even if multiple stents are implanted during the index procedure.

- A patient whose side-branch is treated by XIENCE PRIME SV can be registered. In such a case, main vessel should be treated by XIENCE PRIME.
- A patient who are treated by other DES for planned stent and XIENCE PRIME SV for bail-out purpose cannot be registered.
- Additional revascularization procedures as a part of AE treatment and planned staged procedures will not be considered as another registration, or adverse events.
- A patient who is treated, but failed to be implanted by XIENCE PRIME SV and finally treated by other devices only (No XIENCE PRIME SV are implanted) must also be registered. In such a case, only the stent information, device deficiency information and reportable adverse events related to the PRIME stent, if any, are required to be captured. Follow-up of the patient who does not receive any XIENCE PRIME SV stent is not required.
- A patient may have another lesion(s) that may be treated by larger diameter stent(s). In such a case, treatment by XIENCE PRIME is preferable. Lesion(s) treated by other than XIENCE PRIME is not considered as the target lesion.

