3.1. Statistical analysis environment

Statistical analysis software: SAS Institute Inc., Windows version SAS version 9.4 or later

3.2. Calculation method of various items, etc.

Items	Calculation method, etc.
Summary statistics (consecutive numbers)	Mean, standard deviation, number of specimens, median, Q1, Q3, minimum, maximum and 95% confidence interval of the mean will be calculated. Number of Samples: Displayed as an integer Mean, standard deviation, median, Q1, Q3: displayed to one order of magnitude below the data of interest Minimum and Maximum Values Shown at the Same Digit as the Data Subject
Confidence interval of the mean	Confidence intervals based on t distributions are calculated. $CI = \bar{x} \pm t_{(1-\alpha/2;n-1)} \frac{s}{\sqrt{n}}$

Items	Calculation method, etc.

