Summary statistics (incidence)	
Incidence rates (%), number of events (molecules), number of populations analyzed (denominators) and 95% confidence intervals of frequencies are calculated. However, cases in which the relevant variable is a missing value are also included in the population of the incidence calculation.
 
4.3 Population numbers for antiplatelet therapy and 4.4 adverse events are specified as follows.
 
4.3 Antiplatelet therapy
 
Newly enrolled patients will be included.
 
Pre-procedure: Case of stenting
 
Procedure Day to Discharge Day: Stenting Cases
 
Procedural Day ~ 8 Months Observation Day: 8 Months Analyzed by Case Time Point of Stenting
 
Procedural Day-1 Year Observation Day: 1 Year Analyzed by Time Point of Stent Implantation
 
Procedural Day ~ 2 Years Observation Day: 2 Years Analyzed by Time Point of Stent Implantation
 
Procedural Day ~ 3 Years Observation Day: 3 Years Analyzed by Time Point of Stent Implantation
 
Procedural Day ~ 4 Years Observation Day: 4 Years Analysis Population by Time Point of Stent Implantation
 
Procedural Day ~ 5 Years Observation Day: 5 Years Analysis Population by Time Point of Stent Implantation
 
4.4 Adverse Events
 
Newly enrolled patients will be included.
 
Procedural Day + 3 Day: Stent Case
 
Procedural Day +4 Days or Beyond to Discharge Day: Stenting Cases
 
The day after discharge to the observation day of Month 8: 8 months for analysis by time point of stenting
 
Observation day of 8 months to 1 year: 1 year for analysis by time point of stenting
 
Observation day 1 to 2 years after the observation day of 1 year: 2 years for analysis by time point of stented patients
 
Observation day of 2-year observation day to 3-year observation day: 3 years for analysis by time point of stented patients
 
Observation day of the following day of observation in Year 3 to Year 4: 4 years for analysis by time point of stent implantation
 
Observation day of the following day of observation in Year 4 to Year 5: 5 years for analysis by time point of stenting
 
During hospitalization: patients with stents
 
Until 8 months: Stent implantation
 
Until 1 year: Stent implantation
 
Until 2 years: Cases of stenting
 
Until 3 years: Cases of stenting
 
Until 4 years: Cases of stenting
 
Until the end of the survey: patients undergoing stent placement
 
Overall post-procedure: stenting cases

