
Items	Calculation method, etc.
Confidence interval for the incidence	
Accurate confidence intervals based on Clopper-Pearson method will be calculated.
 $\pi_L = \frac{v_2}{v_2 + v_1 F_{\alpha/2}[v_1, v_2]} \quad v_1 = 2(n - x + 1), v_2 = 2x$ $\pi_U = \frac{v_1 F_{\alpha/2}[v_1, v_2]}{v_2 + v_1 F_{\alpha/2}[v_1, v_2]} \quad v_1 = 2(x + 1), v_2 = 2(n - x)$
Age (years)	The actual age at the date of the procedure (date of registration) is calculated from the date of birth (date is read in one day).
Body Mass Index	Calculated from weight (kg) and height (cm). Body Mass Index = Weight (kg)/ (Height (cm)/100) ²
Acceptable range on the observation day	
Observation day of 8 months: ± 30 days 8 months after the procedure day Observation day 1 year: ± 30 days after the procedure day Observation date of 2 years: ± 30 days 2 years after the procedure date Observation day 3 years: ± 30 days 3 years after the procedure date Observation day in Year 4: ± 30 days 4 years after the procedure date Observation day in 5 years: ± 30 days 5 years after the procedure date
 
However, if it can be confirmed that there is no problem with the data quality, it should be adopted as the data at the time according to the time of the questionnaire, even if it is outside the range.

4. Statistical Analysis Content

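### Interval formulas for device- and lesion-level results ignore several units per patient, so they understate the standard error if outcomes within a patient are positively correlated (minor)

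*SAP*

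**What the plan says.** SAP 3.2 sets one interval method for each type of variable.

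- **Proportions:** "Accurate confidence intervals based on Clopper-Pearson method will be calculated", with n the number of units counted.
- **Means:** "Confidence intervals based on t distributions are calculated", using s/√n and n − 1 degrees of freedom. The interval is part of the standard continuous summary: "Mean, standard deviation, number of specimens, median, Q1, Q3, minimum, maximum and 95% confidence interval of the mean will be calculated".

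SAP 4.2.8 then asks for intervals on three success rates: "Success rates and confidence intervals will be calculated by product for per-device placement (XP_SV only), per-lesion procedure and per-patient XP_SV placement". The Table 15 denominators are:

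- **Row 1:** "Number of devices used by the study population cases"
- **Row 2:** lesions with lesion information collected
- **Row 3:** patients

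Two other places use lesions as the unit. Table 9 (SAP 4.2.2) summarises length, vessel diameter and percent stenosis over all lesions. Table 11-2 (SAP 4.2.4) marks items 1 and 11, both labelled per lesion, for full summary statistics.

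The plan allows for several units per patient. Table 8-1 has rows for one, two, three and four or more target lesions per patient, and Table 11-2 has rows for one, two and three study stents. Protocol 2.2 says: "The observations will be compiled on a per-patient basis even if multiple stents are implanted during the index procedure". It does not say how lesion or device data are reduced to one value per patient. Neither document mentions a clustered variance, a mixed model, resampling by patient or a one-lesion-per-patient rule.

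**The concern.** Lesions and stents in one patient share that patient's anatomy, and those treated at the index procedure share its session and operator. A failed placement in one lesion plausibly makes a second failure in the same patient more likely. The binomial and t formulas in SAP 3.2 count every lesion or device as a separate piece of information. With positive within-patient correlation the effective sample size is smaller than n, the standard error is understated, and the interval can cover less often than its label says.

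The survey tests no hypothesis, so for these rows the estimate and its interval are the whole result. SAP 3.2 presents the proportion intervals as exact, and that property holds only for independent units.

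**Working it through.** **1. The plan's own precision figure.** Protocol 2.3 and SAP 1.3 give a half-width of 4.2% for a 15% MACE rate in 300 patients. Clopper-Pearson for 45/300, by the SAP's F formula, gives 11.16% to 19.55%. The half-width is (19.55 − 11.16)/2 = 4.20%, and 4.20/15 = 28%. The figure reproduces. Its unit is the patient, so within-patient clustering does not touch it.

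**2. Inputs for the clustered rows.** From the documents: about 300 patients, a 95% level, and the two interval formulas. Assumed, because the documents are silent:

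- Units per patient, as shares with 1, 2 and 3 units: 91/8/1% (mean 1.1), 75/20/5% (mean 1.3), 60/30/10% (mean 1.5).
- Within-patient correlation ρ: 0.1, 0.3, 0.5.
- True success rates: 95%, 98%, 99%.

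**3. Formulas.** Design effect D = 1 + (Σm²/Σm − 1)ρ, where m is the number of units in a patient. The standard error ratio is √D. Approximate coverage of a nominal 95% t interval is 2Φ(1.96/√D) − 1. For 60/30/10%, Σm²/Σm = (0.6 + 1.2 + 0.9)/1.5 = 1.8. At ρ = 0.5, D = 1 + 0.8 × 0.5 = 1.40 and √D = 1.183. Coverage is 2Φ(1.657) − 1 = 90.2%.

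Clopper-Pearson coverage was simulated with beta-binomial clusters, 8,000 runs per setting. The Monte Carlo standard error near 95% is √(0.95 × 0.05/8000) = 0.24 points.

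**4. Results.**

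| Mean units | ρ | D | √D | t coverage | Clopper-Pearson coverage at 95 / 98 / 99% success |
|---|---|---|---|---|---|
| 1.1 | 0.1 | 1.020 | 1.010 | 94.8% | 96.0 / 97.4 / 98.0% |
| 1.1 | 0.3 | 1.060 | 1.030 | 94.3% | 96.1 / 97.0 / 97.5% |
| 1.1 | 0.5 | 1.100 | 1.049 | 93.8% | 95.5 / 96.2 / 97.9% |
| 1.3 | 0.1 | 1.054 | 1.027 | 94.4% | 95.3 / 96.5 / 95.8% |
| 1.3 | 0.3 | 1.162 | 1.078 | 93.1% | 94.9 / 95.6 / 94.2% |
| 1.3 | 0.5 | 1.269 | 1.127 | 91.8% | 93.7 / 94.3 / 93.6% |
| 1.5 | 0.1 | 1.080 | 1.039 | 94.1% | 95.2 / 95.4 / 96.8% |
| 1.5 | 0.3 | 1.240 | 1.114 | 92.2% | 94.7 / 94.2 / 95.2% |
| 1.5 | 0.5 | 1.400 | 1.183 | 90.2% | 91.7 / 92.4 / 94.0% |

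With ρ = 0, Clopper-Pearson covers 96.0% to 98.2% in the settings run. This built-in conservatism absorbs mild clustering. The t interval has no such reserve.

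**5. What a reader would see.** Take a success rate near 97%, and adjust by dividing both counts by D.

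- 360 lesions (1.2 per patient: 80% with one, 20% with two), ρ = 0.3, D = 1.10: 349/360 gives 94.6% to 98.5% unadjusted and 94.5% to 98.5% adjusted, about 5% wider.
- 450 lesions (1.5 per patient), ρ = 0.5, D = 1.40: 436/450 gives 94.8% to 98.3% unadjusted and 94.4% to 98.5% adjusted, about 20% wider.

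**The case against.** The strongest reply is that no undercoverage has been shown. Cluster size and correlation are both assumed. The table shells list possible categories and are not forecasts. The study stent comes in a single 2.25 mm diameter (SAP 4.2.7), so one study device per patient may be common. At 1.1 units per patient, Clopper-Pearson meets its nominal level in every setting run. This stands: for the proportions, undercoverage is conditional. It does not rescue the t intervals for lesion means, which fall below nominal throughout the assumed range, though only slightly at the low end.

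Protocol 2.2 might be read as making every analysis per patient. Table 15 rows 1 and 2 are plainly not per patient, and no reduction rule is given.

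Scope also needs care. A reader might infer that the QCA means in Tables Q1 and Q2 are lesion-level and so affected. SAP 4.6 does not state their unit. Table Q2 summarises regions separately, and nothing says regions within a patient are pooled. Tables 12 and 13 speak of proportions of cases, and rows 1 to 5 of Table 8-1 are per patient. None of these can be counted as affected on the text.

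A reader might also infer that these are the central results for re-examination. Protocol 6.1 instead names stent thrombosis and adverse events from antiplatelet medication as the important items, and the sample size rests on patient-level MACE.

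**Conclusion.** The mismatch between formula and unit is in the text for Table 15 rows 1 and 2, Table 9, and Table 11-2 items 1 and 11. If within-patient correlation is positive, the plan understates their standard errors. With 300 patients, 1.1 to 1.5 units per patient and correlation 0.1 to 0.5, all but the patient number being assumptions, the correct standard error is about 1% to 18% larger. Coverage of nominal 95% t intervals runs from about 94.8% down to 90.2%. Clopper-Pearson coverage is at least 95% at about 1.1 units per patient and about 92% at the unfavourable corner.

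The flat statement that all these intervals are too narrow goes further than the documents allow. The consequence is minor: limits move by a few tenths of a percentage point in the examples, no test or decision rule uses these tables, and the per-patient success rate, MACE and the 4.2% half-width are unaffected.

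**What to change.** Add to SAP 3.2 that any interval whose unit is a lesion or device is clustered on patient, for example by a cluster-robust (GEE) variance on the logit scale for proportions, or by resampling patients. Where failures are few, report the wider of that interval and Clopper-Pearson. At 1.3 units per patient there would be 300 × 1.3 = 390 units, and 2% to 5% failure means only about 8 to 20 failures. That is too few to estimate a within-patient correlation reliably, so an interval built on an estimated effective sample size is not a good choice. The simpler alternative is to report these rows without intervals.

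Keep plain Clopper-Pearson for per-patient rows. State the unit of analysis for Tables Q1 and Q2, and apply the same rule if they are analysed per lesion.

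The cost is slightly wider intervals and a little more programming. No new data are needed. Clustering on patient does not deal with correlation between patients at the same site, which is a separate question.

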4.2.9. Hospitalization information

Summary statistics will be calculated for length of stay (days) after the procedure date. In addition, the proportion and confidence interval of relevant patients will be calculated by product for prolongation of hospital stay due to serious adverse events.

Table 16. Hospitalization information

- Analysis set: Stent implantation cases (newly enrolled patients)

4.3. Antiplatelet therapy

4.3.1. Antiplatelet therapy

For antiplatelet therapy, the proportion and confidence interval of the relevant cases will be calculated by product for each observation time point.

No	Time of observation
1	Before the procedure
2	Procedure Day to Discharge Day
3	Procedural date-8 months observation day
4	Procedural date-Observation date of Year 1
5	Procedural date-Observation date for 2 years
6	Procedural date-3 Years Observation Day
7	Procedural date-Observation date, Year 4
8	Procedural date-5 Years Observation Day

Table 17. Antiplatelet therapy (by observation time point)

- Analysis set: Stent implantation cases (newly enrolled patients)

Items

No	Item name
1	Dual antiplatelet therapy [aspirin + clopidogrel, aspirin + ticlopidine]
2	Aspirin, clopidogrel, ticlopidine, cilostazol, and others

4.4. Adverse Events

4.4.1. Adverse events (composite endpoint)

For adverse events (composite endpoint), incidence rates will be calculated by product for each time of onset.

No	Time of onset
1	Procedural day + 3 days from procedure date
2	Procedural Day + Day 4 or later to discharge date
3	Observation day of the day after discharge to Month 8
4	Observation day of Month 8 to Observation day of Year 1
5	Observation day of 1 year to the following day of 2 years
6	Observation day of the following day of Year 2 to Observation day of Year 3
7	Observation day of Year 3 to Year 4
8	Observation day following the observation day of Year 4 to the observation day of Year 5
9	During hospitalization
10	Up to 8 months
11	Until one year
12	Until 2 years
13	Up to 3 years
14	Up to 4 years
15	Until the end of the survey
16	Entire post-procedure

Table 18. Adverse events (composite endpoint, by time of onset)

- Analysis set: Stent implantation cases (newly enrolled patients)

Items [] indicating Breakdown

No	Item name
1	Target Lesion Failure [TLR Based on Cardiac Death, Myocardial Infarction Associated with Target Vessels, and Ischemic Findings].
2	Death + myocardial infarction + revascularization [death, myocardial infarction, revascularization]
3	Target vessel failure [cardiac death, myocardial infarction, TLR based on ischemic findings, TVR (non-TLR) based on ischemic findings, TVR (TLR or TVR (non-TLR)) based on ischemic findings].
4	Major adverse cardiac events (cardiac death, total myocardial infarction, TLR based on ischemic findings)
5	Death or myocardial infarction
6	Cardiac death or myocardial infarction
7	Myocardial infarction related to cardiac death or target vessel

Determination of myocardial infarction is based on the WHO (SPIRIT III) definitions

4.4.2. Adverse Events (by Event)

For adverse events (by event), the incidence rate will be calculated by product for each time of onset.

Table 19. Adverse events (by event and time of onset)

- Analysis set: Stent implantation cases (newly enrolled patients)

Items [] indicating Breakdown

No	Item name
1	Death [cardiac death, death attributable to non-coronary vessels, death not attributable to cardiovascular causes]
2	Myocardial infarction [ST-segment elevation myocardial infarction, non-ST-segment elevation myocardial infarction, Q-wave myocardial infarction, non-Q-wave myocardial infarction]
3	TLR [TLR based on ischemic findings [CABG, PCI], TLR not based on ischemic findings [CABG, PCI].
4	TVR (non-TLR) [TVR (non-TLR) [CABG, PCI] based on ischemic findings, TVR (non-TLR) [CABG, PCI] not based on ischemic findings].
5	TVR (TLR or TVR (non-TLR)) [TVR based on ischemic findings (TLR or TVR (non-TLR)) [CABG, PCI]], TVR not based on ischemic findings (TLR or TVR (non-TLR)) [CABG, PCI]].
6	Non-TVR [CABG, PCI]
7	Total revascularization [revascularization based on ischemic findings [CABG, PCI], revascularization not based on ischemic findings [CABG, PCI].
8	Bleeding

Determination of myocardial infarction is based on the WHO (SPIRIT III) definitions

4.4.3. Adverse events (stent thrombosis)

For adverse events (stent thrombosis), the incidence rate is calculated.

Table 20. Adverse events (stent thrombosis)

- Analysis set: Stent implantation cases (newly enrolled patients)

4.4.4. Adverse events (survival time analysis)

Cumulative incidence is plotted by Kaplan-Meier for the AEs defined below, with the first occurrence as an event and non-occurrence as censored. In addition, the sample size, cumulative incidence, and 95% confidence interval of the cumulative incidence will be calculated for the at-risk population at 240, 365, 730, 1095, 1460, 1825 days, and the entire period.

Figure 21. Adverse events (by survival time analysis event)

- Analysis set: Stent implantation cases (newly enrolled patients)

No	Items	Definitions
1	Event	Death, TLR based on ischemic findings, first occurrence of stent thrombosis as event Use non-event cases as truncation examples
2	Survival time	Event example: Event date-Procedure date + 1 Censored: last contact date or withdrawal date-procedure date + 1

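### Kaplan-Meier with deaths censored modestly overstates the cumulative incidence of TLR and stent thrombosis in SAP 4.4.4, on the likelier reading that each event has its own curve

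*SAP*

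**What the plan says.** SAP 4.4.4 states: "Cumulative incidence is plotted by Kaplan-Meier for the AEs defined below", "with the first occurrence as an event and non-occurrence as censored". Its definition table gives the events in one cell as "Death, TLR based on ischemic findings, first occurrence of stent thrombosis as event" and adds "Use non-event cases as truncation examples". The time for a patient without the event is given by "Censored: last contact date or withdrawal date-procedure date + 1". Estimates with 95% confidence intervals are due for the "at-risk population at 240, 365, 730, 1095, 1460, 1825 days, and the entire period".

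Neither document names death as a competing event or specifies a competing-risk estimator. SAP 4.4.2 shows that deaths of every cause are recorded: "Death [cardiac death, death attributable to non-coronary vessels, death not attributable to cardiovascular causes".

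Separately, SAP 4.4.1 to 4.4.3 plan crude incidences in Tables 18 to 20. SAP 3.2 sets the denominator for their cumulative periods to all stented patients.

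**The concern.** A patient who has died cannot later have a TLR or a stent thrombosis. Under the stated rule, someone who dies free of the event is a non-event case and is censored, as if still able to have the event after leaving observation. The result of 1-KM is then the risk in a hypothetical population in which death does not remove anyone. It is not the proportion of treated patients who have the event, which is what the label cumulative incidence promises.

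Stent thrombosis is the first of the two important evaluation items in Protocol 6.1. Ischemia-driven TLR is a component of the MACE rate on which the survey is sized (Protocol 2.3, SAP 1.3). The error runs in one direction, cannot shrink as follow-up lengthens, and is not reflected in the confidence interval.

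**Working it through.** **1. Which reading applies.** The plural reference to adverse events in the opening sentence of SAP 4.4.4 and the title "Figure 21. Adverse events (by survival time analysis event" point to one curve per event. The single event cell also allows one composite of death, TLR and stent thrombosis. In that case death is an event and nothing competes with it. The rest of the check takes the per-event reading.

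**2. Direction.** At each event time the Aalen-Johansen estimate grows by S_all × d/n and 1-KM grows by S_event × d/n. Here d is the number of events, n the number at risk, S_all the probability of being alive and event-free, and S_event the Kaplan-Meier event-free probability with deaths censored. S_event is never below S_all, so 1-KM is never below the Aalen-Johansen estimate.

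**3. The plan's own precision figure.** SAP 1.3 gives a half-width of 4.2%, or 28% of 15%, for n=300. The Clopper-Pearson interval for 45/300 is 11.16% to 19.55%, so the half-width is (19.55 − 11.16)/2 = 4.2 points, and 4.2/15 = 28%. The figure is reproduced. The same method gives the yardsticks used below:
- 30/300 (10%): 6.85% to 13.97%, half-width 3.6 points.
- 3/300 (1%): 0.21% to 2.89%, half-width 1.3 points.

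**4. Inputs for the size.** The documents state no 5-year rate of death, TLR or stent thrombosis. Assumed: 5-year all-cause mortality of 10% or 20%, Kaplan-Meier TLR of 10%, Kaplan-Meier stent thrombosis of 1.0%.

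**5. Constant hazards over T = 5 years.** With l = −ln(1 − KM)/5 and m = −ln(1 − mortality)/5, the cumulative incidence is

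CIF = l/(l + m) × (1 − exp(−5(l + m))).

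- TLR, 10% mortality: l = m = 0.02107; 0.5 × (1 − 0.90 × 0.90) = 0.5 × 0.19 = 9.50%.
- TLR, 20% mortality: m = 0.04463; 0.3207 × (1 − 0.90 × 0.80) = 0.3207 × 0.28 = 8.98%.
- Stent thrombosis, 10% mortality: l = 0.00201; 0.0871 × (1 − 0.99 × 0.90) = 0.0871 × 0.109 = 0.95%.
- Stent thrombosis, 20% mortality: 0.0431 × (1 − 0.99 × 0.80) = 0.0431 × 0.208 = 0.90%.

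**6. Events concentrated early.** Put 60% of the event's cumulative hazard in year 1 and spread the rest evenly over years 2 to 5, with the death hazard constant. Apply the formula within each period and weight by survival to its start. For TLR with 10% mortality:
- Year 1: event hazard 0.6 × 0.10536 = 0.06322, death hazard 0.02107. Contribution 0.75 × (1 − exp(−0.08429)) = 6.06%.
- Years 2 to 5: event hazard 0.04214, death hazard 0.08429. Contribution 0.9192 × 0.3333 × (1 − exp(−0.12643)) = 3.64%.
- Total 9.70%.

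| Event (KM) | 5-year mortality | Hazard | CIF | Gap (points) | Relative overstatement |
|---|---|---|---|---|---|
| TLR 10% | 10% | constant | 9.50% | 0.50 | 5.3% |
| TLR 10% | 20% | constant | 8.98% | 1.02 | 11.4% |
| TLR 10% | 10% | early | 9.70% | 0.30 | 3.1% |
| TLR 10% | 20% | early | 9.39% | 0.61 | 6.5% |
| Stent thrombosis 1% | 10% | constant | 0.95% | 0.05 | 5.4% |
| Stent thrombosis 1% | 20% | constant | 0.90% | 0.10 | 11.6% |
| Stent thrombosis 1% | 10% | early | 0.97% | 0.03 | 3.2% |
| Stent thrombosis 1% | 20% | early | 0.94% | 0.06 | 6.7% |

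**7. Wider mortality range.** With constant hazards and mortality from 5% to 30%, a Kaplan-Meier TLR of 10% corresponds to 9.75% down to 8.44%. Even the last gap, 1.56 points, is below the 3.6-point half-width.

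**The case against.** The case for leaving this alone is substantial.

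- **It is small.** A gap of 0.05 to 0.10 points on a 1% stent thrombosis rate is 0.15 to 0.3 of one patient in 300, and every gap above is below the sampling error. This stands. It limits the importance of the point, but the bias remains systematic and avoidable.
- **The lower end is likelier for TLR.** Angiography is scheduled at 8 months (Protocol 3 and 5.5), so TLR may well cluster early, and the constant-hazard figures would then be too high. This stands.
- **Other estimates exist.** The crude cumulative rows keep patients who died in the denominator, so a reader does not depend on Figure 21 for either event. This stands.
- **The survey is descriptive.** There is no comparator, performance goal or test, and overstating harm is the cautious direction for safety. This is fair, but a cautious figure should still be labelled as what it is.
- **The curve may be a composite.** The wording is loose enough to allow it. There would then be no competing risk, but also no separate time-to-event estimate for stent thrombosis, so the text needs clarifying either way.

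A reader might also infer that any disagreement between Figure 21 and the crude tables comes from censoring deaths. The documents do not support that. The crude rows count patients lost to follow-up as free of the event, while both Kaplan-Meier and Aalen-Johansen censor them. The crude rows also follow observation days with an adjustable ±30-day window (SAP 3.2), whereas the curves use fixed days. A gap would remain after the fix.

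**Conclusion.** The point holds as a modest one. On the per-event reading, SAP 4.4.4 labels as cumulative incidence a quantity that can only equal or exceed it for ischemia-driven TLR and stent thrombosis. The direction follows from the stated rule. The size rests on assumed rates: with 10% to 20% mortality at 5 years the relative overstatement is about 3% to 12%, nearer the low end if TLR occurs early. In absolute terms that is about 0.3 to 1.0 points on a 10% TLR and at most about 0.1 point on a 1% stent thrombosis.

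A reader might infer that the survey's main efficacy result or its safety conclusion is compromised. The documents do not support this. They do not name TLR as the main efficacy event or give Figure 21 precedence over the tables. The sample size rests on MACE, which is not among the events in SAP 4.4.4, and no decision threshold is set. The point is a worthwhile improvement to reporting, not an error that would overturn a conclusion.

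**What to change.** Revise SAP 4.4.4 to:

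- state that death, ischemia-driven TLR and stent thrombosis each have their own curve;
- estimate TLR and stent thrombosis by Aalen-Johansen with 95% intervals at the same landmark days, treating death as a competing event unless the death is itself counted as the event;
- keep Kaplan-Meier for death;
- show 1-KM for TLR and stent thrombosis as a secondary display, labelled as censoring deaths.

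If the estimator is not changed, the minimum is to relabel the curves as 1-KM with deaths censored and to state how deaths are handled.

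The cost is a few lines of SAP text and a small program change. No new data are needed, because death is already a reportable serious adverse event (Protocol 5.9) and has its own curve. The one drawback is that the main figure will not compare directly with older Kaplan-Meier stent reports, which the secondary display resolves.
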